### 7.8. Treatment After the End of the Study

Insulin lispro (Humalog) and LY900014 will not be made available from the sponsor to subjects after conclusion of the study. Subjects will resume their previous insulin regimen after the study procedure has been completed.

## 8. Discontinuation Criteria

### 8.1. Discontinuation from Study Treatment

Subjects who discontinue the investigational product early will have procedures performed as shown in the Schedule of Activities (Section 2).

#### 8.1.1. *Discontinuation of Inadvertently Enrolled Subjects*

The criteria for enrollment must be followed explicitly. If the investigator site identifies a subject who did not meet enrollment criteria and who was inadvertently enrolled, the sponsor will be notified. If the sponsor identifies a subject who did not meet enrollment criteria and who was inadvertently enrolled, the investigator site will be notified.

If the subject was enrolled but did not receive study drug, the subject will be discharged from the study without receiving study drug; if the subject received the single dose of the study drug prior to realizing the subject did not meet enrollment criteria, they will continue to be monitored per protocol.

### 8.2. Discontinuation from the Study

Subjects will be discontinued under the following circumstances:

- Enrollment in any other clinical trial involving an investigational product or enrollment in any other type of medical research judged not to be scientifically or medically compatible with this study
- Participation in the study needs to be stopped for medical, safety, regulatory, or other reasons consistent with applicable laws, regulations, and good clinical practice (GCP)
- Investigator Decision
  - the investigator decides that the patient should be discontinued from the study
- Subject Decision
  - the patient requests to be withdrawn from the study
- Participation in the study needs to be stopped for safety reasons in the case of a severe hypoglycaemic episode

Subjects who discontinue the study early will have end-of-study procedures performed as shown in the Schedule of Activities (Section 2).

### 8.3. Subjects Lost to Follow-up

A subject will be considered lost to follow-up if he or she repeatedly fails to return for scheduled visits and is unable to be contacted by the study site. Site personnel are expected to make diligent attempts to contact subjects who fail to return for a scheduled visit or were otherwise unable to be followed up by the site.

## 9. Study Assessments and Procedures

Section 2 lists the Schedule of Activities, detailing the study procedures and their timing (including tolerance limits for timing).

Appendix 2 lists the laboratory tests that will be performed for this study.

Appendix 4 provides a summary of the maximum number and volume of invasive samples, for all sampling, during the study.

The specifications in this protocol for the timings of safety and sample collection are given as targets to be achieved within reasonable limits. Modifications may be made to the time points based upon merging clinical information. The scheduled time points may be subject to minor alterations; however, the actual time must be correctly recorded in the electronic CRF (eCRF). Late collection outside the stipulated time allowances or failure to obtain samples due to clinical issues (such as venous access), technical issues (such as equipment problems), or subject defaulting on a scheduled procedure will not be considered as protocol deviations but the site will still be required to notify the sponsor in writing via a file note.

Unless otherwise stated in subsections below, all samples collected for specified laboratory tests will be destroyed within 60 days of receipt of confirmed test results. Certain samples may be retained for a longer period, if necessary, to comply with applicable laws, regulations, or laboratory certification standards.

Investigators must document their review of each laboratory safety report.

### 9.1. Efficacy Assessments

This section is not applicable for this study.

### 9.2. Adverse Events

Investigators are responsible for monitoring the safety of subjects who have entered this study and for alerting Lilly or its designee to any event that seems unusual, even if this event may be considered an unanticipated benefit to the patient.

The investigator is responsible for the appropriate medical care of subjects during the study.

The investigator remains responsible for following, through an appropriate health care option, AEs that are serious or otherwise medically important, considered related to the investigational product or the study, or that caused the patient to discontinue the investigational product before completing the study. The patient should be followed until the event resolves, stabilizes with appropriate diagnostic evaluation, or is reasonably explained. The frequency of follow-up evaluations of the AE is left to the discretion of the investigator.

After the informed consent form (ICF) is signed, study site personnel will record, via eCRF, the occurrence and nature of each patient's preexisting conditions, including clinically significant signs and symptoms of the disease under treatment in the study. Additionally, site personnel will record any change in the condition(s) and the occurrence and nature of any AEs.

The investigator will interpret and document whether or not an AE has a reasonable possibility of being related to study treatment or a study procedure, taking into account the disease, concomitant treatment, or pathologies.

A “reasonable possibility” means that there is a cause and effect relationship between the investigational product, study device, and/or study procedure and the AE.

Planned surgeries should not be reported as AEs unless the underlying medical condition has worsened during the course of the study.

If a patient’s investigational product is discontinued as a result of an AE, study site personnel must report this to Lilly or its designee via eCRF.

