### **9.2.1. Serious Adverse Events**

An SAE is any AE from this study that results in 1 of the following:

- death
- initial or prolonged inpatient hospitalization
- a life-threatening experience (that is, immediate risk of dying)
- persistent or significant disability/incapacity
- congenital anomaly/birth defect
- events considered significant by the investigator based upon appropriate medical judgment

Study site personnel must alert Lilly, or its designee, of any SAE within 24 hours of investigator awareness of the event via a sponsor-approved method. If alerts are issued via telephone, they are to be immediately followed with official notification on study-specific SAE forms. This 24-hour notification requirement refers to the initial SAE information and all follow-up SAE information.

Although all AEs are recorded in the eCRF after signing informed consent, SAE reporting begins after the patient has signed informed consent and has received the investigational product. However, if an SAE occurs after signing informed consent, but prior to receiving investigational product, AND is considered reasonably possibly related to a study procedure then it MUST be reported.

Investigators are not obligated to actively seek AEs or SAEs in subjects once they have discontinued from and/or completed the study (the patient summary CRF has been completed). However, if the investigator learns of any SAE, including a death, at any time after a subject has been discharged from the study, and he/she considers the event reasonably possibly related to the study treatment or study participation, the investigator must promptly notify Lilly.

Pregnancy (maternal or paternal exposure to the investigational product) does not meet the definition of an AE. However, to fulfill regulatory requirements any pregnancy should be reported following the SAE process to collect data on the outcome for both mother and fetus.

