#### **9.2.1.1. Suspected Unexpected Serious Adverse Reactions**

Suspected unexpected serious adverse reactions (SUSARs) are serious events that are not listed in the IB and that the investigator identifies as related to the investigational product or procedure. US 21 Code of Federal Regulations 312.32 and European Union Clinical Trial Directive 2001/20/EC and the associated detailed guidances or national regulatory requirements in participating countries require the reporting of SUSARs. Lilly has procedures that will be followed for the recording and expedited reporting of SUSARs that are consistent with global regulations and the associated detailed guidances.

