### **10.3.1. Safety Analyses**

#### **10.3.1.1. Clinical Evaluation of Safety**

All investigational and protocol procedure AEs will be listed, and if the frequency of events allows, safety data will be summarized using descriptive methodology.

The incidence of symptoms for each treatment will be presented by severity and by association with investigational product as perceived by the investigator. Symptoms reported to occur prior to enrollment will be distinguished from those reported as new or increased in severity during the study. Each symptom will be classified by the most suitable term from the Medical Dictionary for Regulatory Activities.

The number of investigational product-related SAEs will be reported.

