9.5 Safety and Tolerability Assessments

9.5.1 Adverse events

Where changes in severity are recorded in the Case Report Form (CRF), each separate severity of the adverse event (AE) will be reported in the listings, only the most severe will be used in the summary tables. A pre-existing condition is defined as an AE that starts before the patient has provided written informed consent and is ongoing at consent. A non-treatment emergent AE is defined as an AE which starts after informed consent but prior to dosing. A treatment-emergent AE is defined as an AE which occurs postdose or which is present prior to dosing and becomes more severe postdose.

All AEs will be listed. Treatment-emergent AEs will be summarized by treatment, age group, severity and relationship to the study drug. The frequency (the number of adverse events, the number of patients experiencing an adverse event and the percentage of patients experiencing an adverse event) of treatment-emergent adverse events will be summarized by treatment, age group, Medical Dictionary for Regulatory Activities (MedDRA) version 19.1 system organ class and preferred term. The summary and frequency adverse event tables will be presented for all causalities and those considered related to the study drug. Any serious adverse events will be tabulated.

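### Protocol 9.2 defines a reasonable possibility of relatedness as an existing causal relationship, so events that are only possibly related may be recorded as not related

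*Protocol*

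**What the plan says.** **The question.** In Protocol 9.2 (Adverse Events) the investigator documents "whether or not an AE has a reasonable possibility of being related to study treatment or a study procedure". The answer is yes or no.

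**The definition.** The sentence that follows explains the key term. A reasonable possibility "means that there is a cause and effect relationship between the investigational product, study device, and/or study procedure and the AE". Nothing in it softens the statement to a possible, potential or suspected relationship.

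**Where the judgement is used.**
- Protocol 9.2 makes the investigator follow an AE to resolution, stabilisation or explanation if it is serious or medically important, is considered related, or led to discontinuation of the product.
- Protocol 9.2.1 (Serious Adverse Events) makes two reports conditional on relatedness. An SAE after consent but before the product is given is reportable if it "is considered reasonably possibly related to a study procedure then it MUST be reported". An SAE learned of after discharge is reportable if "he/she considers the event reasonably possibly related to the study treatment or study participation".
- Protocol 9.2.1.1 defines SUSARs as serious, unlisted events "that the investigator identifies as related to the investigational product or procedure".
- Protocol 10.3.1.1 presents symptoms by the investigator's view of association, and states: "The number of investigational product-related SAEs will be reported".
- SAP 9.5.1 states: "The summary and frequency adverse event tables will be presented for all causalities and those considered related to the study drug".

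**The concern.** A possibility that a relationship exists and the existence of that relationship are different thresholds. Section 9.2 sets the first in its question and the second in its definition, and section 9.2.1 returns to the first. An investigator cannot tell from the text which applies.

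The difference matters because causation is hard to establish for a single event here. Each subject gets one blinded injection per period, after basal insulin has been withdrawn or stopped, often after a glulisine run-in, and then undergoes a clamp of up to 10 hours. Many events could have more than one plausible cause and would meet the possibility standard but not the certainty standard.

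At stake are the outputs and duties that rest on the relatedness judgement. AEs are the only endpoint listed for the safety objective, and the related subset is one of the two ways in which the SAP tabulates them.

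**Working it through.** No stated figure depends on this point, so there is nothing to recompute. The check sets the definition against the question and follows both through to their uses.

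**Step 1: which events are classified differently.** Sort AEs by the strength of the causal evidence.

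| Evidence for a causal link | Answer under the 9.2 question | Answer under the 9.2 definition |
|---|---|---|
| Established | Related | Related |
| Possible, not established | Related | Not related |
| No reasonable possibility | Not related | Not related |

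Only the middle row changes. Because the recorded answer is binary, there is no intermediate category in which such an event could stay visible as possibly related.

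**Step 2: direction.** Every event that meets the definition also meets the question, so the number related under the literal definition cannot exceed the number related under the question. Any error is toward too few related events.

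**Step 3: what depends on the answer.**

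| Item | Effect of a middle-row event scored not related |
|---|---|
| SAP 9.5.1 related-AE tables | Event missing |
| Protocol 10.3.1.1 count of product-related SAEs | SAE not counted |
| Protocol 9.2.1.1 SUSAR definition | Investigator's label may not be applied |
| Protocol 9.2 follow-up duty | Could lapse if the event is also not serious, not medically important and did not cause discontinuation |
| Protocol 9.2.1 pre-dose and post-discharge triggers | Affected only if the phrase used there is read through the 9.2 definition |
| SAP 9.5.1 listing of all AEs and all-causality tables of treatment-emergent AEs | None |
| Protocol 9.2.1 notification of any post-dose SAE within 24 hours | None; not conditional on relatedness |
| Primary PK analysis and sample size | None |

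**Step 4: size.** The denominators are known: up to 42 + 42 = 84 subjects and 84 × 2 = 168 injections. The numerator is not. Neither document gives an expected AE rate or the share of events that would fall in the middle row, so no under-count can be calculated.

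**The case against.** The strongest reply is that the question put to the investigator is a possibility question, to be answered by judgement in light of the disease, concomitant treatment and other pathology. Both conditional triggers in 9.2.1 also use possibility wording. An investigator who follows the surrounding text would mark a possibly related event as related, and the definition would do no harm.

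There are also safeguards:
- The safety endpoint in Table ITRR.1 is AEs, not related AEs. All AEs are listed, and SAEs are tabulated.
- Post-dose SAEs reach the sponsor within 24 hours whatever their causality, and Protocol 9.4.7.1.1 makes every severe hypoglycaemic episode an SAE with no relatedness test.
- The sponsor reviews SAEs and AE trends (9.4.7), its study team is unblinded (7.3), and it states that its SUSAR procedures are consistent with global regulations (9.2.1.1).
- Both treatments are judged by the same definition under subject and investigator blinding, so no bias between treatments is shown.

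These arguments stand as limits on the harm. They do not remove the contradiction, and they leave the related-only tables, the related-SAE count, the follow-up duty and the two conditional triggers exposed.

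A reader might go further and infer that nearly every AE will be recorded as not related, that the related-AE table could be emptied, or that serious reactions will escape SUSAR screening. The documents do not support this. They give no rates, and some foreseeable events, such as pain immediately after injection or injection-site reactions, could be attributed even on a strict standard. The sponsor's SUSAR procedures are not reproduced, so a failure of them cannot be shown.

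**Conclusion.** The point holds as an error in an operative rule. The definition in 9.2 contradicts the question it serves and the wording of 9.2.1. Followed as written, it scores a merely possible event as not related. Misclassification is a risk of literal reading, not a certain outcome, because some investigators will answer the question as asked.

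The consequence is a possible under-count in the related-AE tables and the product-related SAE count, with a possible effect on the SUSAR label, the follow-up duty and the two conditional SAE triggers. The effect on those triggers rests on the further assumption that the 9.2 definition governs the phrase used in 9.2.1, which the protocol does not say. The direction is known; the size is not. No all-causality safety result and no PK or GD conclusion depends on it. It should be corrected because related-event tables are hard to interpret when the threshold behind them is stated in two incompatible ways.

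**What to change.** In Protocol 9.2, reword the definition so that a reasonable possibility means that a cause and effect relationship with the product, device or procedure is possible or suspected, and need not be established. Add a statement that the phrase used for the two triggers in 9.2.1, and the word related in 9.2.1.1, carry the same threshold. The table specifications in SAP 9.5.1 can stay as they are, since they take the investigator's judgement as given.

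The cost is one reworded sentence, one cross-reference and a note in site training. No additional data, visits or analyses are needed. The downside is that somewhat more events may be tabulated as related. If causality has already been recorded under the present wording, the clinical study report should say which definition was in force.

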### **9.2.1. Serious Adverse Events**

An SAE is any AE from this study that results in 1 of the following:

- death
- initial or prolonged inpatient hospitalization
- a life-threatening experience (that is, immediate risk of dying)
- persistent or significant disability/incapacity
- congenital anomaly/birth defect
- events considered significant by the investigator based upon appropriate medical judgment

Study site personnel must alert Lilly, or its designee, of any SAE within 24 hours of investigator awareness of the event via a sponsor-approved method. If alerts are issued via telephone, they are to be immediately followed with official notification on study-specific SAE forms. This 24-hour notification requirement refers to the initial SAE information and all follow-up SAE information.

Although all AEs are recorded in the eCRF after signing informed consent, SAE reporting begins after the patient has signed informed consent and has received the investigational product. However, if an SAE occurs after signing informed consent, but prior to receiving investigational product, AND is considered reasonably possibly related to a study procedure then it MUST be reported.

Investigators are not obligated to actively seek AEs or SAEs in subjects once they have discontinued from and/or completed the study (the patient summary CRF has been completed). However, if the investigator learns of any SAE, including a death, at any time after a subject has been discharged from the study, and he/she considers the event reasonably possibly related to the study treatment or study participation, the investigator must promptly notify Lilly.

Pregnancy (maternal or paternal exposure to the investigational product) does not meet the definition of an AE. However, to fulfill regulatory requirements any pregnancy should be reported following the SAE process to collect data on the outcome for both mother and fetus.

#### **9.2.1.1. Suspected Unexpected Serious Adverse Reactions**

Suspected unexpected serious adverse reactions (SUSARs) are serious events that are not listed in the IB and that the investigator identifies as related to the investigational product or procedure. US 21 Code of Federal Regulations 312.32 and European Union Clinical Trial Directive 2001/20/EC and the associated detailed guidances or national regulatory requirements in participating countries require the reporting of SUSARs. Lilly has procedures that will be followed for the recording and expedited reporting of SUSARs that are consistent with global regulations and the associated detailed guidances.

#### **9.2.2. Complaint Handling**

Lilly collects product complaints on investigational products and drug delivery systems used in clinical trials in order to ensure the safety of study participants, monitor quality, and to facilitate process and product improvements.

Subjects should be instructed to contact the investigator as soon as possible if he or she has a complaint or problem with the investigational product (or drug delivery system) so that the situation can be assessed.

### **9.3. Treatment of Overdose**

For the purposes of this study, an overdose of LY900014 or Humalog is considered any dose higher than the dose assigned through randomization.

Excess insulin administration may cause hypoglycaemia and hypokalemia. Mild episodes of hypoglycaemia usually can be treated with oral glucose. More severe episodes with coma, seizure, or neurologic impairment may be treated with intramuscular/SC glucagon or concentrated IV glucose. Sustained carbohydrate intake and observation may be necessary because hypoglycaemia may recur after apparent clinical recovery. Hypokalemia must be corrected appropriately.

### **9.4. Safety**

#### **9.4.1. Physical Examinations**

Physical examinations and routine medical assessments will be conducted as specified in the Schedule of Activities (Section 2) and as clinically indicated.

#### **9.4.2. Body Weight**

Body weight will be recorded as specified in the Schedule of Activities (Section 2) and as clinically indicated.

### **9.4.3. Hip and Waist Circumference**

Hip and waist circumference will be recorded as specified in the Schedule of Activities (Section 2). The average of triplicate measurements of waist (narrowest circumference between lowest aspect of the ribs and anterior superior iliac crests) and the hip (widest circumference between the anterior superior iliac crests and the greater trochanters) circumference will be measured.

### **9.4.4. Laboratory Tests**

Laboratory tests detailed in [Appendix 2](#) should be conducted according to the Schedule of Activities (Section 2).

### **9.4.5. Vital Signs**

For each patient, vital sign measurements should be conducted according to the Schedule of Activities (Section 2) and as clinically indicated.

